## Safety Data

Tables in this section are based on the safety population unless otherwise stated.

Table 14.3.1.1.1	Summary of Adverse Events –Part A
Table 14.3.1.1.2	Summary of Adverse Events – Part B
Table 14.3.1.1.3	Summary of Adverse Events – Overall
Table 14.3.1.2.1	Summary of Study Product Use-Emergent Adverse Events by System Organ Class and MedDRA Preferred Term – Part A
Table 14.3.1.2.2	Summary of Study Product Use-Emergent Adverse Events by System Organ Class and MedDRA Preferred Term – Part B
Table 14.3.1.2.3	Summary of Study Product Use-Emergent Adverse Events by System Organ Class and MedDRA Preferred Term – Overall
Table 14.3.1.3.1	Summary of Serious Study Product Use-Emergent Adverse Events by System Organ Class and MedDRA Preferred Term – Part A
Table 14.3.1.3.2	Summary of Serious Study Product Use-Emergent Adverse Events by System Organ Class and MedDRA Preferred Term – Part B
Table 14.3.1.3.3	Summary of Serious Study Product Use-Emergent Adverse Events by System Organ Class and MedDRA Preferred Term – Overall
Table 14.3.1.4.1	Summary of Study Product Use-Emergent Adverse Events by System Organ Class, MedDRA Preferred Term and Severity – Part A
Table 14.3.1.4.2	Summary of Study Product Use-Emergent Adverse Events by System Organ Class, MedDRA Preferred Term and Severity – Part B
Table 14.3.1.4.3	Summary of Study Product Use-Emergent Adverse Events by System Organ Class, MedDRA Preferred Term and Severity – Overall
Table 14.3.1.5.1	Summary of Study Product Use-Emergent Adverse Events by System Organ Class, MedDRA Preferred Term and Relationship – Part A
Table 14.3.1.5.2	Summary of Study Product Use-Emergent Adverse Events by System Organ Class, MedDRA Preferred Term and Relationship – Part B
Table 14.3.1.5.3	Summary of Study Product Use-Emergent Adverse Events by System Organ Class, MedDRA Preferred Term and Relationship – Overall
Table 14.3.2.1	Listing of Deaths, Other Serious and Significant Adverse Events
Table 14.3.2.2	Listing of Adverse Events Leading to Discontinuation
Table 14.3.4.1	Summary of General Biochemistry
Table 14.3.4.2	Summary of Hematology
Table 14.3.4.3	Summary of Urinalysis
Table 14.3.4.4	Listing of Abnormal On-Study Laboratory Values
Table 14.3.4.5	Listing of Clinically Significant On-Study Laboratory Values
Table 14.3.5.1	Summary of Vital Signs Values
Table 14.3.5.2	Listing of Abnormal On-Study Vital Signs Values
Table 14.3.5.3	Listing of Clinically Significant On-Study Vital Signs Values
Table 14.3.6.1	Summary of ECG Assessments
Table 14.3.6.2	Listing of Abnormal On-Study ECG Assessments
Table 14.3.6.3	Listing of Clinically Significant On-Study ECG Assessments
Table 14.3.7.1	Listing of Abnormal On-Study Physical Examination
Table 14.3.7.2	Listing of Clinically Significant On-Study Physical Examination

## PLANNED LISTINGS

Listing 16.1.7	Listing of Randomization
Listing 16.2.1	Listing of Study Completions
Listing 16.2.2.1	Listing of Blood Sampling Time Deviations
Listing 16.2.2.2	Listing of Protocol Deviations
Listing 16.2.2.3	Listing of Inclusion/Exclusion Criteria Violations
Listing 16.2.3	Listing of Analysis Populations
Listing 16.2.4.1	Listing of Demographic Characteristics
Listing 16.2.4.2	Listing of Medical History
Listing 16.2.4.3	Listing of Prior Medication
Listing 16.2.4.4	Listing of Tobacco Use History
Listing 16.2.4.5	Listing of Contraceptive Methods (Female Subjects)
Listing 16.2.5.1.1	Listing of VLN Cigarette Product Use Part A
Listing 16.2.5.1.2	Listing of Usual Brand Cigarette Product Use Part A
Listing 16.2.5.1.3	Listing of Gum Product Use Part A
Listing 16.2.5.2.1	Listing of First VLN Cigarette Product Use Part B
Listing 16.2.5.2.2	Listing of First Usual Brand Cigarette Product Use Part B
Listing 16.2.5.2.3	Listing of First Gum Product Use Part B
Listing 16.2.5.3.1	Listing of Second VLN Cigarette Product Use Part B
Listing 16.2.5.3.2	Listing of Second Usual Brand Cigarette Product Use Part B
Listing 16.2.5.3.3	Listing of Second Gum Product Use Part B
Appendix 16.2.6.1	Questionnaires Responses
Listing 16.2.6.1.1	Listing of Use the Product Again Responses
Listing 16.2.6.1.2	Listing of Tobacco/Nicotine Withdrawal Questionnaire Responses
Listing 16.2.6.1.3	Listing of Direct Effects of Product Questionnaire Responses
Listing 16.2.6.1.4	Individual Tobacco/Nicotine Withdrawal Questionnaire Response Profiles (Controlled Use) – Linear Scale
Listing 16.2.6.1.5	Individual Tobacco/Nicotine Withdrawal Questionnaire Response Profiles (Uncontrolled Use) – Linear Scale
Listing 16.2.6.1.6	Individual Tobacco/Nicotine Withdrawal Questionnaire Reduction in VAS Score Profiles (Controlled Use) – Linear Scale
Listing 16.2.6.1.7	Individual Tobacco/Nicotine Withdrawal Questionnaire Reduction in VAS Score Profiles (Uncontrolled Use) – Linear Scale
Listing 16.2.6.1.8	Individual Direct Effects of Product Questionnaire Response Profiles (Controlled Use) – Linear Scale
Listing 16.2.6.1.9	Individual Direct Effects of Product Questionnaire Response Profiles (Uncontrolled Use) – Linear Scale
Listing 16.2.6.2.1	Listing of Tobacco/Nicotine Withdrawal Questionnaire Effect Parameters
Listing 16.2.6.2.2	Listing of Direct Effects of Product Questionnaire Effect Parameters
Listing 16.2.6.3.1.1	Listing of Unadjusted Plasma Nicotine Concentration (Controlled Use)
Listing 16.2.6.3.1.2	Listing of Unadjusted Plasma Nicotine Concentration (Uncontrolled Use)
Listing 16.2.6.3.2.1	Listing of Baseline-Adjusted Plasma Nicotine Concentration (Controlled Use)
Listing 16.2.6.3.2.2	Listing of Baseline-Adjusted Plasma Nicotine Concentration (Uncontrolled Use)
Listing 16.2.6.3.3	Listing of Baseline-Adjusted Plasma Nicotine Pharmacokinetic Parameters
Listing 16.2.6.3.4	Listing of Nicotine Actual Sampling Time
Listing 16.2.6.3.5	Individual Unadjusted Plasma Nicotine Concentration Profiles (Controlled Use) – Linear Scale
Listing 16.2.6.3.6	Individual Unadjusted Plasma Nicotine Concentration Profiles (Controlled Use) – Semi-Log Scale
Listing 16.2.6.3.7	Individual Unadjusted Plasma Nicotine Concentration Profiles (Uncontrolled Use) – Linear Scale

Listing 16.2.6.3.8	Individual Unadjusted Plasma Nicotine Concentration Profiles (Uncontrolled Use) – Semi-Log Scale
Listing 16.2.6.3.9	Individual Baseline-Adjusted Plasma Nicotine Concentration Profiles (Controlled Use) – Linear Scale
Listing 16.2.6.3.10	Individual Baseline-Adjusted Plasma Nicotine Concentration Profiles (Controlled Use) – Semi-Log Scale
Listing 16.2.6.3.11	Individual Baseline-Adjusted Plasma Nicotine Concentration Profiles (Uncontrolled Use) – Linear Scale
Listing 16.2.6.3.12	Individual Baseline-Adjusted Plasma Nicotine Concentration Profiles (Uncontrolled Use) – Semi-Log Scale
Listing 16.2.7	Listing of Adverse Events
Listing 16.2.8.1	Listing of General Biochemistry
Listing 16.2.8.2	Listing of Hematology
Listing 16.2.8.3	Listing of Serology
Listing 16.2.8.4	Listing of Urine Drug Screen
Listing 16.2.8.5	Listing of Urinalysis
Listing 16.2.8.6	Listing of Other Laboratory Tests (Endocrinology)
Listing 16.2.9.1	Listing of Concomitant Medication
Listing 16.2.9.2	Listing of General Physical Examination
Listing 16.2.9.3	Listing of Vital Signs
Listing 16.2.9.4	Listing of ECG Assessments

## APPENDIX A

### STUDY SCHEDULE

	Screening	Check-in	Part A	Part B												End of Study/ET		
Day:	-28 to -2	-1	1 to 3	4 to 6 (Daily controlled use and uncontrolled use sessions)												6		
Assessment				Assessment timepoints (minutes a )														
Informed consent	X																	
Demographics	X																	
Medical history	X																	
Review of eligibility	X	X																
Physical examination	X	X b														X b		
Height, weight, BMI	X																	
HIV, Hepatitis B/C	X																	
Pregnancy test	X c	X d																

NOTE: Pre-use assessments (not including PK) may be conducted up to 60 minutes prior to product use. When assessments coincide at any given timepoint during a product use session, the order of assessments should be pharmacodynamics assessments followed by PK. The pharmacodynamic assessments should be conducted at the nominal timepoint ( $\pm 2$  minutes up to 30 minutes postdose and  $\pm 5$  minutes postdose thereafter). AE=adverse event; BMI=body mass index; ECG=electrocardiogram; ET=early termination; FSH=follicle stimulating hormone; HIV=human immunodeficiency virus; pre=pre-use

a All listed timepoints are minutes after the start of product use

b Abbreviated (symptom-directed) physical examination performed at the investigator's discretion

c Serum pregnancy test

d Urine pregnancy test

	Screening	Check-in	Part A	Part B												End of Study/ET	
Day:	-28 to -2	-1	1 to 3	4 to 6 (Daily controlled use and uncontrolled use sessions)												6	
Assessment	Assessment timepoints (minutes a )																
FSH (post-menopausal women)	X																
Vital signs e	X	X															X
Oral temperature	X	X															X
12-lead ECG	X																X
Urine cotinine screen	X																
Urine drug and alcohol test	X	X															
Clinical laboratory tests f	X																X
Concomitant medications	X	X	X	<----- Recorded throughout ----->													X
AE Monitoring g	X	X	X	<----- Recorded throughout ----->													X
Randomization			pre h	pre i													

e Vital signs include respiratory rate, pulse rate and blood pressure

f Clinical laboratory assessments include hematology, biochemistry, and urinalysis

g Spontaneous AE reporting is continuous throughout the study, beginning with the time the subject gives informed consent; however, at regular intervals, AE checks will be performed using a non-leading question.

h Day 1 only

i Day 4 only

	Screening	Check-in	Part A	Part B													End of Study/ET
Day:	-28 to -2	-1	1 to 3	4 to 6 (Daily controlled use and uncontrolled use sessions)													6
Assessment	Assessment timepoints (minutes a )																
Product use		X j	X k	<0 l	-	-	-	>									
PK sampling m			pre	2	5	7	10	12	15	20	30	45	60	90	120	150	180
Pharmacodynamic Training/practice n		X															
Tobacco/Nicotine Withdrawal Questionnaire o			pre		5				15		30		60	90			
Direct Effects of Product Questionnaire o			pre		5				15		30		60	90			
Use the product again VAS			X p											90 o			

j Trial of 4 mg nicotine polacrilex gum for 10 minutes

k Product use under ad libitum condition for 4 hours on each day

l First product under controlled use condition manner (10 puffs [maximum  $3 \pm 2$  seconds per puff] with approximately 30-second inter-puff-intervals for cigarettes and 10 minutes “chew and park” for nicotine polacrilex gum) and second product under uncontrolled use condition for approximately 10 minutes (ad libitum) with approximately 6 hours in between 1st and 2nd use sessions

m Blood samples collected at same time points following the start of the 1st and 2nd product use sessions. Pre-product use samples should be collected within approximately 5 minutes prior to the start of product use, all other time points should be taken within  $\pm 1$  minute for the first 30 minutes and  $\pm 5$  minutes from the nominal time for all other time points (except when coinciding with PD testing). Actual time of blood draw will be recorded.

n Additional PD training sessions may be performed throughout the study, as necessary.

o Administered at same time points following the start of the 1st and 2nd product use sessions

p Questionnaire administered at end of each product use session, within 10 minutes of completing the product use session (i.e., 4 hours  $\pm 10$  minutes)

	Screening	Check-in	Part A	Part B										
Day:	-28 to -2	-1	1 to 3	4 to 6 (Daily controlled use and uncontrolled use sessions)										
Assessment	Assessment timepoints (minutes a )													
Amount of product used			X q		< r	-	-	-	-	>				
Tobacco cessation information														X
Admission		X												
Discharge														X

q Number of units consumed and duration of gum in mouth

r Uncontrolled Product Use Sessions only; number of inhalations per cigarette, duration of inhalations [per puff], duration of gum in mouth

## APPENDIX B

---

### TABLE SHELLS

Table 14.1.1.1  
Summary of Subject Disposition  
(All Subjects)

			Sequence 1	Etc	Overall
Subjects Enrolled [N]					xx
Subjects Randomized [N]			xx	xx	xx
Subjects Who Received Study Product [n(%)]	Study Day 1	Yes	xx (xx.x)	xx (xx.x)	
		No	xx (xx.x)	xx (xx.x)	
	Etc.	Yes	xx (xx.x)	xx (xx.x)	
		No	xx (xx.x)	xx (xx.x)	
	Study Day 6	Yes	xx (xx.x)	xx (xx.x)	
		No	xx (xx.x)	xx (xx.x)	
Subjects Who Completed the Study [n(%)]	Yes		xx (xx.x)	xx (xx.x)	xx (xx.x)
	No		xx (xx.x)	xx (xx.x)	xx (xx.x)
If No, Reason for Early Withdrawal [n(%)]	Reason 1		xx (xx.x)	xx (xx.x)	xx (xx.x)
	Reason 2		xx (xx.x)	xx (xx.x)	xx (xx.x)
	Etc.		xx (xx.x)	xx (xx.x)	xx (xx.x)
Subjects Included in Randomized Population (Part A) [n(%)]			xx (xx.x)	xx (xx.x)	xx (xx.x)
Subjects Included in Randomized Population (Part B) [n(%)]			xx (xx.x)	xx (xx.x)	xx (xx.x)
Subjects Included in Safety Population [n(%)]			xx (xx.x)	xx (xx.x)	xx (xx.x)
Subjects Included in Pharmacodynamic Population [n(%)]			xx (xx.x)	xx (xx.x)	xx (xx.x)
Subjects Included in Pharmacokinetic Population [n(%)]			xx (xx.x)	xx (xx.x)	xx (xx.x)
Subjects Included in Completer Population [n(%)]			xx (xx.x)	xx (xx.x)	xx (xx.x)

Note(s): The percentages are based on the number of randomized subjects;

Date: VERSION - YYYY-MM-DD

Data Source: XXXX

Program Source: XXXXX.sas

Similar Tables:

Table 14.1.1.2	Summary of Subject Disposition (Randomized Population [Part A])
Table 14.1.1.3	Summary of Subject Disposition (Randomized Population [Part B])
Table 14.1.1.4	Summary of Subject Disposition (Safety Population)
Table 14.1.1.5	Summary of Subject Disposition (Pharmacodynamic Population)
Table 14.1.1.6	Summary of Subject Disposition (Pharmacokinetic Population)
Table 14.1.1.7	Summary of Subject Disposition (Completer Population)

Table 14.1.2.1  
Summary of Demographic Characteristics  
(Randomized Population [Part A])

		Sequence 1 (N=XX)	Etc (N=XX)	Overall (N=XX)
Age (years)	N	xx	xx	xx
	Mean (SD)	xx (xx.x)	xx (xx.x)	xx (xx.x)
	Median	xx.x	xx.x	xx.x
	Min, Max	xx, xx	xx, xx	xx, xx
Gender [n(%)]	MALE	xx (xx.x)	xx (xx.x)	xx (xx.x)
	FEMALE	xx (xx.x)	xx (xx.x)	xx (xx.x)
Ethnicity [n(%)]	HISPANIC/LATINO	xx (xx.x)	xx (xx.x)	xx (xx.x)
	NOT HISPANIC/NOT	xx (xx.x)	xx (xx.x)	xx (xx.x)
	LATINO			
Race [n(%)]	RACE1	xx (xx.x)	xx (xx.x)	xx (xx.x)
	RACE2	xx (xx.x)	xx (xx.x)	xx (xx.x)
	Etc.	xx (xx.x)	xx (xx.x)	xx (xx.x)
	MULTIPLE RACE	xx (xx.x)	xx (xx.x)	xx (xx.x)
Weight (kg)	N	xx	xx	xx
	Mean (SD)	xx (xx.x)	xx (xx.x)	xx (xx.x)
	Median	xx.x	xx.x	xx.x
	Min, Max	xx, xx	xx, xx	xx, xx
Height (cm)	N	xx	xx	xx
	Mean (SD)	xx (xx.x)	xx (xx.x)	xx (xx.x)
	Median	xx.x	xx.x	xx.x
	Min, Max	xx, xx	xx, xx	xx, xx
Body Mass Index (kg/m  )	N	xx	xx	xx
	Mean (SD)	xx (xx.x)	xx (xx.x)	xx (xx.x)
	Median	xx.x	xx.x	xx.x
	Min, Max	xx, xx	xx, xx	xx, xx

Date: VERSION - YYYY-MM-DD

Data Source: XXXX

Program Source: XXXXX.sas

Similar Tables:

Table 14.1.2.2	Summary of Demographic Characteristics (Randomized Population [Part B])
Table 14.1.2.3	Summary of Demographic Characteristics (Safety Population)
Table 14.1.2.4	Summary of Demographic Characteristics (Pharmacodynamic Population)
Table 14.1.2.5	Summary of Demographic Characteristics (Pharmacokinetic Population)
Table 14.1.2.6	Summary of Demographic Characteristics (Completer Population)

Table 14.1.3  
Summary of Tobacco Use History  
(Safety Population)

Tobacco Product		Product Trial (N=XX)	Overall (N=XX)
Number of Tobacco Product Used Per Day	Cigarette		
	N	xx	xx
	Mean (SD)	xx (xx.x)	xx (xx.x)
	Median	xx.x	xx.x
	Min, Max	xx, xx	xx, xx
	Etc...		
	N	xx	xx
	Mean (SD)	xx (xx.x)	xx (xx.x)
	Median	xx.x	xx.x
	Min, Max	xx, xx	xx, xx
Duration of Tobacco Product Using	Cigarette (years)		
	N	xx	xx
	Mean (SD)	xx (xx.x)	xx (xx.x)
	Median	xx.x	xx.x
	Min, Max	xx, xx	xx, xx
	Etc...		
	N	xx	xx
	Mean (SD)	xx (xx.x)	xx (xx.x)
	Median	xx.x	xx.x
	Min, Max	xx, xx	xx, xx

Programming Note: Duration of Tobacco Product Using = number of years between tobacco use start date and end date.

Date: VERSION - YYYY-MM-DD

Data Source: XXXX

Program Source: XXXXX.sas

Table 14.1.4.1  
Summary of Product Use Part A  
(Safety Population)

	Study Product A	Study Product B	Study Product C
Number of Product Used			
N	xx	xx	xx
Mean (SD)	xx (xx.x)	xx (xx.x)	xx (xx.x)
Median	xx.x	xx.x	xx.x
Q1, Q3	xx, xx	xx, xx	xx, xx
Min, Max	xx, xx	xx, xx	xx, xx
Duration of Product Use			
N	xx	xx	xx
Mean (SD)	xx (xx.x)	xx (xx.x)	xx (xx.x)
Median	xx.x	xx.x	xx.x
Q1, Q3	xx, xx	xx, xx	xx, xx
Min, Max	xx, xx	xx, xx	xx, xx

Date: VERSION - YYYY-MM-DD

Data Source: XXXX

Program Source: XXXXX.sas

Table 14.1.4.2  
Summary of Second Product Use Part B  
(Safety Population)

	Study Product A	Study Product B	Study Product C
Total Number of Inhalations per Subject	N Mean (SD) Median Q1, Q3 Min, Max	xx xx (xx.x) xx.x xx, xx xx, xx	xx xx (xx.x) xx.x xx, xx xx, xx
Duration of Inhalations	N Mean (SD) Median Q1, Q3 Min, Max	xx xx (xx.x) xx.x xx, xx xx, xx	xx xx (xx.x) xx.x xx, xx xx, xx
Average Duration of Inhalations per Subject	N Mean (SD) Median Q1, Q3 Min, Max	xx xx (xx.x) xx.x xx, xx xx, xx	xx xx (xx.x) xx.x xx, xx xx, xx
Total Duration of Inhalations per Subject	N Mean (SD) Median Q1, Q3 Min, Max	xx xx (xx.x) xx.x xx, xx xx, xx	xx xx (xx.x) xx.x xx, xx xx, xx
Duration of Gum Product Use	N Mean (SD) Median Q1, Q3 Min, Max		xx xx (xx.x) xx.x xx, xx xx, xx

Programming Note: The N for Duration of Inhalations = Total puff count of the product group.  
N for Average and Total Duration of Inhalations per Subject = Number of subjects in each product group.

Table 14.3.1.1.1  
Summary of Adverse Events - Part A  
(Safety Population)

Parameter	Study Product A (N=XX)	Study Product B (N=XX)	Study Product C (N=XX)	Part A Overall (N=XX)
Adverse Events Reported [n]				
Subjects With At Least One AE [n(%)] [1]				
Study Product Use-Emergent Adverse Events (SPUEAEs) Reported [n]	xx	xx	xx	xx
Subjects With At Least One SPUEAE [n(%)] [1]	xx (xx.x)	xx (xx.x)	xx (xx.x)	xx (xx.x)
SPUEAEs Relationship [2]				
Not Related [n(%)]	xx (xx.x)	xx (xx.x)	xx (xx.x)	xx (xx.x)
Unlikely [n(%)]	xx (xx.x)	xx (xx.x)	xx (xx.x)	xx (xx.x)
Possible [n(%)]	xx (xx.x)	xx (xx.x)	xx (xx.x)	xx (xx.x)
Likely [n(%)]	xx (xx.x)	xx (xx.x)	xx (xx.x)	xx (xx.x)
Definitely [n(%)]	xx (xx.x)	xx (xx.x)	xx (xx.x)	xx (xx.x)
SPUEAEs Severity/Intensity [2]				
Mild [n(%)]	xx (xx.x)	xx (xx.x)	xx (xx.x)	xx (xx.x)
Moderate [n(%)]	xx (xx.x)	xx (xx.x)	xx (xx.x)	xx (xx.x)
Severe [n(%)]	xx (xx.x)	xx (xx.x)	xx (xx.x)	xx (xx.x)
Study Product Use-Emergent Serious Adverse Events (SPUESAEs) Reported [n] [2]	xx	xx	xx	xx
Subjects With At Least One SPUESAE [n(%)] [1]	xx (xx.x)	xx (xx.x)	xx (xx.x)	xx (xx.x)
SPUEAEs Leading To Study Discontinuation Reported [n] [2]	xx (xx.x)	xx (xx.x)	xx (xx.x)	xx (xx.x)
SPUEAEs Leading To Death Reported [n] [2]	xx (xx.x)	xx (xx.x)	xx (xx.x)	xx (xx.x)

[1] Percentages are based on the number of subjects in the Safety Population in each Study Product group.

[2] Percentages are based on the total number of Study Product Use-Emergent adverse events reported in each Study Product group.

Date: VERSION - YYYY-MM-DD

Data Source: XXXX

Program Source: XXXXX.sas

Table 14.3.1.1.2  
Summary of Adverse Events - Part B  
(Safety Population)

Parameter	Study Product A (N=XX)	Study Product B (N=XX)	Study Product C (N=XX)	Part B Overall (N=XX)
Study Product Use-Emergent Adverse Events (SPUEAEs) Reported [n]	xx	xx	xx	xx
Subjects With At Least One SPUEAE [n(%)] [1]	xx (xx.x)	xx (xx.x)	xx (xx.x)	xx (xx.x)
SPUEAEs Relationship [2]				
Not Related [n(%)]	xx (xx.x)	xx (xx.x)	xx (xx.x)	xx (xx.x)
Unlikely [n(%)]	xx (xx.x)	xx (xx.x)	xx (xx.x)	xx (xx.x)
Possible [n(%)]	xx (xx.x)	xx (xx.x)	xx (xx.x)	xx (xx.x)
Likely [n(%)]	xx (xx.x)	xx (xx.x)	xx (xx.x)	xx (xx.x)
Definitely [n(%)]	xx (xx.x)	xx (xx.x)	xx (xx.x)	xx (xx.x)
SPUEAEs Severity/Intensity [2]				
Mild [n(%)]	xx (xx.x)	xx (xx.x)	xx (xx.x)	xx (xx.x)
Moderate [n(%)]	xx (xx.x)	xx (xx.x)	xx (xx.x)	xx (xx.x)
Severe [n(%)]	xx (xx.x)	xx (xx.x)	xx (xx.x)	xx (xx.x)
Study Product Use-Emergent Serious Adverse Events (SPUESAEs) Reported [n] [2]	xx	xx	xx	xx
Subjects With At Least One SPUESAE [n(%)] [1]	xx (xx.x)	xx (xx.x)	xx (xx.x)	xx (xx.x)
SPUEAEs Leading To Study Discontinuation Reported [n] [2]	xx (xx.x)	xx (xx.x)	xx (xx.x)	xx (xx.x)
SPUEAEs Leading To Death Reported [n] [2]	xx (xx.x)	xx (xx.x)	xx (xx.x)	xx (xx.x)

[1] Percentages are based on the number of subjects in the Safety Population in each Study Product group.

[2] Percentages are based on the total number of Study Product Use-Emergent adverse events reported in each Study Product group.

Date: VERSION - YYYY-MM-DD

Data Source: XXXX

Program Source: XXXXX.sas

Similar Table:

Table 14.3.1.1.3 Summary of Adverse Events - Overall

Table 14.3.1.2.1  
Summary of Study Product Use-Emergent Adverse Events by System Organ Class and MedDRA Preferred Term – Part A  
(Safety Population)

System Organ Class MedDRA Preferred Term	Study Product A (N=XX)		Study Product B (N=XX)		Study Product C (N=XX)	
	Subjects [n(%)]	Events [n]	Subjects [n(%)]	Events [n]	Subjects [n(%)]	Events [n]
Any SPUEAE	xx (xx.x)	xx	xx (xx.x)	xx	xx (xx.x)	xx
System Organ Class 1	xx (xx.x)	xx	xx (xx.x)	xx	xx (xx.x)	xx
MedDRA Term 11	xx (xx.x)	xx	xx (xx.x)	xx	xx (xx.x)	xx
MedDRA Term 12	xx (xx.x)	xx	xx (xx.x)	xx	xx (xx.x)	xx
MedDRA Term 13	xx (xx.x)	xx	xx (xx.x)	xx	xx (xx.x)	xx
System Organ Class 2	xx (xx.x)	xx	xx (xx.x)	xx	xx (xx.x)	xx
MedDRA Term 21	xx (xx.x)	xx	xx (xx.x)	xx	xx (xx.x)	xx
MedDRA Term 22	xx (xx.x)	xx	xx (xx.x)	xx	xx (xx.x)	xx
MedDRA Term 23	xx (xx.x)	xx	xx (xx.x)	xx	xx (xx.x)	xx
Etc.	xx (xx.x)	xx	xx (xx.x)	xx	xx (xx.x)	xx

Note(s): For the subject counts, each Study Product Use-Emergent adverse event is counted only once for each subject within each System Organ Class and MedDRA Preferred Term.

Date: VERSION - YYYY-MM-DD

Data Source: XXXX

Program Source: XXXXX.sas

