### Safety Endpoints

- AEs (incidence, frequency, severity and relationship to product), SAEs, and AEs leading to discontinuation;
- Vital signs (heart rate, blood pressure, respiratory rate, oral temperature);
- 12-lead ECG;
- Clinical laboratory tests (clinical chemistry, hematology, urinalysis);
- Physical examination (complete and brief) findings;
- Concomitant medications.

The details of the safety endpoints' assessment are presented in [Section 10](#).

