### Sample Size Determination

Sample size estimation was performed on both pharmacodynamic endpoints.

Using a 2-sided Type I error rate at  $\alpha=0.05$  and assuming a mean difference in  $E_{max\_urge(\text{controlled})}$  between own-brand cigarette and nicotine polacrilex gum of 15.85 points and standard deviation (SD) of 28.44, 54 completed subjects will be required to detect a significant difference between own-brand cigarette and nicotine polacrilex gum with greater than 80% power. Using a 2-sided Type I error rate at  $\alpha=0.05$  and assuming a mean difference in  $E_{max\_plst(\text{controlled})}$  between own-brand cigarette and nicotine polacrilex gum of 35.21 points and SD of 31.82, estimate based on data obtained from the study site, 16 completed subjects will be adequate to detect a significant difference between own-brand cigarette and nicotine polacrilex gum with greater than 80% power.

An appropriate number of subjects will be randomized on Day 1 (Part A) to ensure that a minimum of 54 subjects complete the study. Replacement subjects may be enrolled to ensure that the minimum number of subjects complete the study.

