### Adverse Events

An adverse event (AE) is any untoward medical occurrence in a clinical investigation subject administered a product and may not necessarily have a causal relationship with the administered treatment. An AE can, therefore, be any unfavorable and unintended sign (including a clinically significant laboratory abnormality), symptom, or disease temporally associated with the use of an investigational product, whether or not related to the investigational product.

A study product use-emergent adverse event (SPUEAE) is defined as an AE that is starting or worsening at the time of or after study product administration (excluding product trial). An AE that occurs during the washout period between study products is considered study product use emergent to the last study product given.

SPUEAEs will be assigned to a product based on the time of occurrence in relation to the last product used prior to the onset of the SPUAE. SPUAEs will be assigned using the following rules:

- SPUAE will be assigned to the last product used by the subject where the date and time of the last product use is on or before of the start date and time of the event. Such assignment will be performed irrespective of any washout period between the start and stop dates of the SPUEAE.
- Any SPUEAE started after the discharge and during the follow-up period will be assigned to the last product that the subject has used during last cycle.

As an overall summary of AEs, the following will be presented by product use and overall in each part and by product use and overall regardless the study part:

- Number of reported AEs;
- Number and percentage of subjects experiencing AEs;
- Number of reported SPUEAEs;
- Number and percentage of subjects experiencing SPUEAEs;
- Number and percentage of SPUEAEs by relationship to study product;
- Number and percentage of SPUEAEs by severity;
- Number of reported study product use-emergent serious adverse events (SPUSAES);
- Number and percentage of subjects experiencing SPUSAES;
- Number and percentage of subjects experiencing SPUEAEs leading to discontinuation; and
- SPUEAEs with an outcome of death.

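### The AE summary shells count discontinuation by events, apparently as a share of all emergent AEs, where SAP section 10 specifies subjects

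*SAP*

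**What the plan says.** AEs leading to discontinuation are a named safety endpoint. SAP section 4 (Safety Endpoints) lists "AEs (incidence, frequency, severity and relationship to product), SAEs, and AEs leading to discontinuation", and protocol section 10.8 agrees. SAP section 10 (Adverse Events) then sets out the overall AE summary by product, for each part and across parts. One item is "Number and percentage of subjects experiencing SPUEAEs leading to discontinuation".

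SAP Appendix B holds the shells that implement this summary. In Tables 14.3.1.1.1 and 14.3.1.1.2 the only row on the topic is "SPUEAEs Leading To Study Discontinuation Reported [n] [2". Its cells are laid out as a count followed by a bracketed figure to one decimal. Table 14.3.1.1.3 is listed as similar to the Part B shell.

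The two footnotes set different denominators:

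- Footnote [2], attached to this row: "Percentages are based on the total number of Study Product Use-Emergent adverse events reported in each Study Product group".
- Footnote [1], attached to the subject-level rows: "Percentages are based on the number of subjects in the Safety Population in each Study Product group".

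The same shells do give a subject-level row for serious events, "Subjects With At Least One SPUESAE [n(%)] [1" (footnote [1]).

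**The concern.** Section 10 and the shells describe different statistics. The numerator changes from subjects to events, and the denominator implied by the cells and footnote [2] changes from subjects to emergent AEs. A programmer who builds from the shell will not produce what section 10 specifies.

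Events over all events does not measure the risk of stopping. For a fixed number of subjects who stop, it falls as the product causes more AEs of any kind. It rises if one subject has several events recorded as leading to withdrawal. In a crossover where the safety reading is a comparison of products, a difference in this percentage could reflect only the number of AEs per product.

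**Working it through.** The plan states no figure for this item, so there is none to reproduce. The check compares text with shell and then works the arithmetic.

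**1. Is a percentage planned?** The row label says [n] only. Footnote [2] does not settle the matter, because the row counting serious emergent AEs also carries [2] and has plain count cells. The discontinuation row differs from that row in having cells for a count and a percentage. The cells and the footnote together imply a percentage of SPUEAEs, although the label does not say so.

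**2. Is the event basis a general convention of these shells?** No. Subject-level rows with footnote [1] exist for any SPUEAE and any serious SPUEAE in both shells, and for any AE in the Part A shell. Section 10 itself frames relationship, severity and fatal outcome by SPUEAE, so an event basis in those rows is not a conflict. For discontinuation, section 10 says subjects.

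**3. Does another planned SAP table supply the figure?** No.

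- Table 14.3.2.2 is a listing, with no counts or denominators.
- The disposition shells (14.1.1.1 to 14.1.1.7) give withdrawal reasons by sequence, not by product.
- The tables by system organ class, severity and relationship do not separate events that led to discontinuation.
- Protocol section 12.4.1 promises a summary of discontinued subjects by the product they last used and by reason. No SAP table implements it, although SAP section 12 declares no changes from the protocol.

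**4. Arithmetic.** Let S be the subjects stopping because of an AE on a product, D the events leading to discontinuation, E all SPUEAEs on that product, and N the subjects using it.

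- Shell basis: D / E.
- Section 10 basis: S / N.

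Inputs: N = 54 is assumed for every product, borrowed from the planned "a minimum of 54 subjects complete the study" (SAP section 4). S, D and E are assumptions, with E taken over a range because the documents give no AE counts. With one event per subject stopping (D = S):

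| E (assumed) | S = 1, shell | S = 2, shell |
|---|---|---|
| 5 | 1/5 = 20.0% | 2/5 = 40.0% |
| 10 | 1/10 = 10.0% | 2/10 = 20.0% |
| 20 | 1/20 = 5.0% | 2/20 = 10.0% |
| 40 | 1/40 = 2.5% | 2/40 = 5.0% |
| 60 | 1/60 = 1.7% | 2/60 = 3.3% |

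On the section 10 basis the result is 1/54 = 1.9% for S = 1 and 2/54 = 3.7% for S = 2, whatever E is.

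For the same number of subjects stopping, a product with 5 SPUEAEs shows 20.0 / 2.5 = 8 times the percentage of a product with 40. The shell figure can lie above or below the subject percentage: at E = 60 it is slightly lower.

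**5. Double counting.** One subject with two events leading to discontinuation, among 10 SPUEAEs, prints as 2/10 = 20.0%. With one such event among 10 it would be 10.0%. The subject percentage is 1.9% either way.

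**The case against.** Several counter-arguments deserve weight.

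- **The body text is already right.** Section 10 specifies the correct statistic and the shell fails to match it. That stands: this is an internal inconsistency, not a deliberate choice of an event-based analysis.
- **The label says [n], so perhaps only a count will be printed.** This is possible, and the percentage cells may be left over from a template. If so, the denominator problem disappears. The count would still be of events, and the subject number and percentage required by section 10 would still be absent.
- **Shells are templates.** SAP section 13 allows slight changes of format and layout without an SAP update. A different numerator and denominator for a named endpoint is not a slight layout change.
- **The information is available elsewhere.** Table 14.3.2.2 identifies subject and product for each case, so a reader could recount by hand, though without denominators. Protocol section 12.4.1 promises something close to the missing figure, but the SAP does not carry it through.
- **The consequences are limited.** This stands. Safety is summarised descriptively, and no test or decision rule uses this row.

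A reader might go further and infer that the shell would reverse the ordering of products, or make VLN look worse than gum. The documents do not support that. They give no AE counts by product and no expectation of which product will have more. The illustration holds the number stopping equal and shows equal risks made to look unequal. Counts could be chosen that change the order, but nothing in the plan makes them likely.

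**Conclusion.** The inconsistency is real. Section 10 calls for subjects with an emergent AE leading to discontinuation, by product. All three summary tables omit that row and give events instead, in a layout that implies a percentage of all SPUEAEs. No other table in the SAP supplies the figure.

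The size depends on AE counts the documents do not give. Over an assumed 5 to 60 SPUEAEs per product, one subject stopping with one event prints as anything from 20.0% to 1.7%, against 1.9% on an assumed 54 subjects. These figures apply only if the cells and footnote govern rather than the [n] label. The events-for-subjects mismatch does not depend on that condition or on any assumed count.

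The primary pharmacodynamic and the pharmacokinetic analyses are unaffected. The shells should be corrected before the tables are programmed, because the AE summary is where the SAP says this endpoint will be read by product.

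**What to change.** In Tables 14.3.1.1.1, 14.3.1.1.2 and 14.3.1.1.3:

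1. Add a row *Subjects With At Least One SPUEAE Leading To Study Discontinuation [n(%)] [1]*.
2. Keep the event row if wanted, as a count only, with no percentage in its cells and no footnote [2].
3. Extend footnote [1] to say that the denominator is Safety Population subjects who used that product in that part or, for the Overall table, in either part. The present wording does not mention part, and a by-part definition alone would not fit the Overall table.

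The relationship, severity and death rows can keep their event basis, which agrees with section 10.

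The cost is an edit to the shells and the table program. The data are already collected, and neither the design nor any other analysis changes.
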